4.2 Study Outcome Measures

For all CGM-related outcome measures, data will be assessed in the following ways:

- Baseline CGM data for both study arms will come from the 14-day, blinded, FreeStyle Libre Pro sensors and readers using the Libre 2 algorithm
- 3-month Post-Dietary Change CGM data (end of month three data) will come from:
 - CGM Arm: 14-day, FreeStyle Libre 2 data download from LibreView
 - BGM Arm: 14-day, blinded, FreeStyle Libre Pro sensors and readers using the Libre 2 algorithm
- 6-month Follow-Up period CGM data (end of month six data) will come from:
 - CGM Arm: 14-day, FreeStyle Libre 2 data download from LibreView
 - BGM Arm: 14-day, blinded, FreeStyle Libre Pro sensors and readers using the Libre 2 algorithm

The blinded FreeStyle Libre Pro reader used for collecting outcome measures data will use the Libre 2 algorithm to keep outcome measure data comparable between study arms.

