	Commercially approved Precision Xtra Blood Glucose & Ketone Monitoring System used for fingerstick ketone monitoring and as indicated for glucose monitoring; used in accordance with package inserts.
--	--

8 Study Intervention

The intervention will compare the impact of two glucose monitoring methods, BGM or CGM, as part of Virta Health's diabetes care program. All care and education are provided via telemedicine (i.e., virtually) and with the use of web-based software applications for biomarker reporting, monitoring, and communication with Virta's care team.

As part of standard Virta Treatment, participants will receive continuous coaching from the Virta care team that focuses on modifying daily nutrition choices to achieve and sustain nutritional ketosis as measured by blood BHB 0.5-3.0 mmol/L. The care team includes health coaches for day-to-day program guidance and HCPs for medication management and clinical oversight. Virta HCPs review glucose values reported by participants in the Virta app. HCPs make proactive and reactive medication dose adjustments to prevent hypoglycemia while participants are experiencing metabolic improvements. Care for Virta participants is provided continuously and is not limited by specific time milestones (e.g., appointments are not at scheduled timepoints).

The current Virta Treatment relies on BGM for glucose assessment and does not supply CGMs as part of routine care. Thus, the intervention under study is use of CGM compared to BGM (Virta's current standard care) for glucose monitoring.

In the BGM arm, participants, health coaches, and Virta HCPs will use BGM and ketone data to guide medication management decisions and to encourage program adherence, per their usual practices. The blinded Libre Pro CGM data collected at baseline and during the intervention and follow-up periods will not be available to participants or the Virta care team; however, data from the blinded Libre Pro CGM assessments can be made available to BGM arm participants after study completion, upon request from the participant. BGM and ketone data will be used to help determine which foods, behaviors, and medications sustain nutritional ketosis. Typical BGM assessment in the Virta Treatment includes one to two fingerstick glucose tests per day depending on the participant's medication regimen. Fingerstick data is reported in the Virta app by the participant.

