
#2: Month 1 Assessment: Day 30 to 44 with up to +/- 10 days
 
Intervention Period
	
 ● Participants complete month 1 assessments ● BGM group: 
 ○ Prompted to apply and start Libre Pro CGM for 14-day wear ○ Participant confirms five days of blinded CGM data has been recorded. If a participant is not able to obtain a minimum of five days of blinded CGM data, they will be provided an option to repeat the blinded sensor wear period. ○ Participant promptly mails blinded CGM sensor back for data capture ● CGM group: 
 ○ Maintains consistent personal Libre 2 use for 14 days ○ HCP documents CGM data review and shares learnings with participant asynchronously ● Additional glucose and ketone monitoring supplies sent as needed ● Month 1 assessments are documented

#3: Month 2 Assessment: Day 60 to 74 with up to +/- 10 days
 
Intervention Period
	
 ● Participants complete month 2 assessments ● BGM group: 
 ○ Prompted to apply and start Libre Pro CGM for 14-day wear ○ Participant confirms five days of blinded CGM data has been recorded. If a participant is not able to obtain a minimum of five days of blinded CGM data, they will be provided an option to repeat the blinded sensor wear period. ○ Participant promptly mails blinded CGM sensor back for data capture

CGM vs. BGM to Optimize Glycemic Outcomes in T2D Following the Virta Treatment Ver. 2.0 06Dec2022

	
 ● CGM group: 
 ○ Maintains consistent personal Libre 2 use for 14 days ○ HCP documents CGM data review and shares learnings with participant asynchronously ● Additional glucose and ketone monitoring supplies sent as needed ● Month 2 assessments are documented

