A participant can choose to terminate study participation and exit the study at any time and for any reason. A participant can be withdrawn from the study without their consent if deemed necessary based on adverse event(s) or for any other reason deemed appropriate by Investigators, such as non-compliance with study instructions. If a participant chooses early termination or is withdrawn, the Investigators will decide whether the participant could be eligible to complete a final assessment.

Participants will be asked their reason for early withdrawal and reason for CGM discontinuation if applicable. Participants who terminate or are withdrawn early will be required to return used blinded Libre Pro CGM sensors and the associated Libre Pro reader promptly after study exit; they will not be required to return any other study-provided glucose or ketone monitoring supplies. Early termination or participant withdrawal will not impact participation in the Virta Treatment.

10 Lost to Follow-Up

Multiple attempts will be made to contact participants who become lost to follow-up. Investigator discretion will determine whether a participant should be withdrawn if reasonable attempts for contact are unsuccessful.

11 Protocol Deviation

A protocol deviation occurs when the study is not conducted according to this protocol. All deviations will be documented in study deviation log. Investigators will not knowingly deviate from this protocol except in the cases of protecting participant safety. The delegated Investigator will notify the IRB of protocol deviations in accordance with IRB policies and procedures.

12 Potential Risks and Benefits

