15.1 Analysis of Primary Endpoint

Summary statistics (including number, mean, median, standard deviation, minimum and maximum) for percentage (%) of TIR (glucose 70 - 180 mg/dL), based on 14-day CGM assessments, will be calculated by treatment and period.

The primary endpoint will be analyzed using a linear mixed model with treatment (BGM or CGM), period (Baseline (period A) and Post-Dietary Change (period B)), and interaction between treatment and period as fixed effects, and patient as random effect. The model will be fitted to all the data simultaneously and from this model the relevant treatment differences will be estimated. Adjusted mean estimates for each treatment with standard errors, the adjusted estimate of treatment mean difference with standard error and a 95 % confidence interval for the treatment mean difference will be provided. The statistical test will be two-sided tests at a nominal 5% significance level.

Enrolled participants without adequate Baseline blinded Libre Pro CGM data will not be included in the analysis. Adequate Baseline blinded CGM data is defined as a minimum of 5 days of sensor data. In cases where two blinded sensors are worn in the same contact period, sensor data may be combined.

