Appendix A. Study Schematic

Appendix B. Study Periods and Assessments

Appendix C. Participant-Facing Materials

17.1 Appendix A. Study Schematic

17.2 Appendix B. Study Periods and Assessments

CGM vs. BGM to Optimize Glycemic Outcomes in T2D Following the Virta Treatment Ver. 2.0 06Dec2022

Study Period	Baseline	Diet Change	Post-Dietary Change / Intervention			Follow-Up
			30 to 44 +/-10	60 to 74 +/-10	90 to 104 +/-10	
Study Day	-21 to -1	0				
Assessment (Contact #)	Baseline Assessment (Contact 1)		Month 1 Assessment (Contact 2)	Month 2 Assessment (Contact 3)	Month 3 Assessment (Contact 4)	Month 6 Assessment (Contact 5)
Demographic Data	X					
14-Day Baseline Blinded CGM	X					
Personal Libre 2 CGM Use (CGM arm only)		←		X	→	
14-Day CGM Data Download (CGM arm only)			X	X	X	X
14-Day Blinded CGM Wear & Data Download (BGM arm only)			X	X	X	X
Ketones 2x/Day		←		X	→	
HbA1c	X				X	X
Medication Use	X		X	X	X	X
ASA-24 (single recall)	X		X	X	X	X
Height	X					
Weight/BMI	X		X	X	X	X
Diabetes Distress Survey	X				X	X
Lifestyle Change Survey					X	X
CGM Satisfaction Survey (CGM arm only)					X	
Participant Contacts with Virta			X	X	X	X
Adverse Events		←		X	→	

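### Month 1 and 2 CGM time in range is collected in both arms but left out of the primary model; using it is a cheap, minor safeguard against dropout that differs by arm

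*Combined protocol and SAP*

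**What the plan says.** **Primary model.** Section 15.1 specifies a "linear mixed model with treatment (BGM or CGM), period (Baseline (period A) and Post-Dietary Change (period B", with treatment, period and their interaction as fixed effects and a patient random effect.

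**What the second period contains.** Section 4.2 settles this: "3-month Post-Dietary Change CGM data (end of month three data) will come from" Libre 2 downloads in the CGM arm and blinded Libre Pro sensors in the BGM arm. Section 15.1 says the model is fitted to all data at once, and Section 5 runs the Post-Dietary Change period from Day 0. Neither brings in earlier records, because period has two levels and Section 4.2 defines the second.

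**What is collected.** In Section 8.4 the BGM group is, at Months 1 and 2 as well as Month 3, "Prompted to apply and start Libre Pro CGM for 14-day wear". The CGM group keeps up 14 days of Libre 2 use at the same visits. Appendix B marks "14-Day CGM Data Download (CGM arm only") and the matching blinded wear in the BGM arm at Months 1, 2, 3 and 6. No CGM outcome in Sections 4.2.1 to 4.2.3 uses the Month 1 or 2 readings.

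**Dropout.** Sections 7.2 and 15.5 expect about 15% loss by Month 3. Under Section 9, after early exit "the Investigators will decide whether the participant could be eligible to complete a final assessment"; the plan does not say whether that assessment counts as Month 3. Section 15 states no missing-data assumption.

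**The concern.** A two-period likelihood model keeps a leaver's baseline value and predicts the missing Month 3 value from baseline alone. That is adequate if, given baseline, leaving is unrelated to later TIR. If people with poor early TIR leave more often, the remaining participants look too good at Month 3. The excess cancels between arms when the dependence and the amount of loss are the same in both, and not otherwise.

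Some dependence is plausible in both arms. In the BGM arm, "Typical BGM assessment in the Virta Treatment includes one to two fingerstick glucose tests per day" (Section 8), so participants see their glucose; the CGM arm sees it continuously. Section 9 also allows withdrawal "for any other reason deemed appropriate by Investigators, such as non-compliance with study instructions". Unequal dependence is possible because the arms get different feedback: only in the CGM arm does Section 8.4 require at Months 1 and 2 that the "HCP documents CGM data review and shares learnings with participant asynchronously".

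At stake is a small shift in the Month 3 contrast. The Month 1 and 2 records that could reduce it are already scheduled.

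**Working it through.** **1. The plan's own figures (Section 15.5: difference 10, SD 20, two-sided 5%, power 80%).** n = 2 × (1.96 + 0.84)² × (20/10)² = 62.8, so 63 per arm as stated. 63/0.85 = 74.1, so about 75 per arm. The standard error at 63 per arm is 20 × √(2/63) = 3.56. A 15% loss from 75 is about 11 leavers per arm.

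**2. Mechanism.** Use SD units, with visits 0 to 3 for Baseline and Months 1 to 3. Suppose leaving after Month 1 depends on Month 1 TIR, so stayers average d above the whole arm at Month 1. Their Month 3 mean is then too high by r13·d and their baseline mean by r01·d. The planned model sees everyone's baseline and takes back about r03·r01·d. What remains between arms is

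error ≈ 20 × (r13 − r01·r03) × (d_CGM − d_BGM).

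For leaving after Month 2, replace r13 and r01 by r23 and r02. Equal slopes and equal loss make the two d values equal, so the error is zero.

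**3. One case by hand.** Assumed, not in the documents: r01 = 0.50, r02 = 0.45, r03 = 0.40, r13 = 0.70, r23 = 0.80; logistic dropout with log-odds slope 1 per 20 TIR points in the CGM arm and 0.5 in the BGM arm; 15% loss in each.

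- Integrating the logistic curve over a normal TIR, leavers average 0.751 SD (slope 1) and 0.412 SD (slope 0.5) below the arm mean.
- d = 0.15 × 0.751/0.85 = 0.133 and 0.15 × 0.412/0.85 = 0.073, a gap of 0.060.
- After Month 1: 20 × (0.70 − 0.50 × 0.40) × 0.060 = 0.60.
- After Month 2: 20 × (0.80 − 0.45 × 0.40) × 0.060 = 0.74.
- Half of the loss at each visit: about 0.67. Simulation with 75 per arm and true effect 10 gives a planned estimate of 10.68.

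**4. Range.** Simulated error over three assumed correlation sets (baseline to later visits 0.40–0.65, between later visits 0.50–0.80). The sign follows the arm with the steeper or larger loss.

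| Assumed dropout | Planned model | Four-visit, unstructured |
|---|---|---|
| Equal slopes, equal loss | about 0 | about 0 |
| Slopes 0.5 vs 0.25, 15% loss | 0.3–0.4 | within about 0.1 |
| Slopes 1 vs 0.5 or 2 vs 1, 15% loss | 0.4–0.9 | within about 0.1 |
| Slope 1 in both, loss 12% vs 18% | 0.4–0.6 | within about 0.1 |
| Slopes 1 vs 0.5 or 2 vs 1, on the next, unrecorded TIR | 0.6–0.9 | 0.3–0.6 |

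Other correlation patterns and slope gaps of 0.25 to 1.0 give about 0.15 to 1.9. A deliberately extreme case, with slope 2 in one arm and none in the other, reaches 2.4.

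**5. Consequences in the moderate case.** For slopes 1 vs 0.5 or 2 vs 1, with standard errors of 3.1 to 3.8:

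- With no true effect, the planned test rejects 4.6–5.1% of the time.
- If BGM dropout is steeper, power is 69–87% planned against 77–91% with four visits.
- If CGM dropout is steeper, nominal power rises. In the step 3 correlation set, 10.68/3.75 − 1.96 = 0.89 gives 81% planned, against 78% with four visits (9.98/3.64 − 1.96 = 0.78).
- If dropout is random, the four-visit model cuts variance by 2–6%, worth 1–3 points of power.

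**6. Limits of the remedy.** If half of the leavers exit before Month 1 in a TIR-dependent way, 0.12 to 0.43 points remain with four visits. Adding visits but keeping only a patient random effect leaves −0.09 to 0.43. Unless all post-baseline correlations equal the baseline ones, it also reports too small a standard error (3.12–3.24 against 3.40–3.67 unstructured).

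**The case against.** The strongest reply is that nothing here is wrong. The model matches the objective in Section 4.1, the outcome in Section 4.2.1 and the data definition in Section 4.2, and it retains leavers' baseline values. The study describes itself as non-pivotal. The moderate-case error is about 0.1 to 0.3 standard errors (0.3/3.56 = 0.08; 0.9/3.1 = 0.29) and well below the 5-point change that Section 3.1 calls clinically meaningful. No correlation, slope or dropout timing is given in the documents. Section 8 has providers reviewing reported glucose in both arms, and withdrawal for non-compliance applies to both, so unequal dependence is conjecture.

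All of this stands, and it fixes the weight of the point as minor. It does not remove the reason to act: BGM participants are asked for two extra 14-day blinded wears whose results enter no stated outcome, while the planned analysis leans on a stronger dropout assumption than the scheduled data require.

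A reader might go further and infer that the primary analysis is invalid, or that the CGM effect will be overstated by a known amount. The documents support neither. They do not say that dropout will differ by arm or in which direction, and the error is zero when slopes and loss are equal. A reader might also infer a systematic loss of power; its sign depends on which arm's dropout is steeper.

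**Conclusion.** The concern holds as a cheap improvement, not as an error in the endpoint. Month 1 and 2 TIR is scheduled in both arms and unused, so leavers after those visits normally count through baseline only. Under assumed, moderate differences between arms the Month 3 contrast shifts by about 0.3 to 0.9 points either way; wider assumptions give about 0.15 to 2. In the moderate case there is no material type I inflation.

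It would be too strong to say that a four-visit model corrects dropout bias in general. It removes the error for leavers who have Month 1 or 2 data and whose dropout depends on recorded TIR. It only reduces the error when dropout depends on unrecorded TIR, and it does not address TIR-dependent exit before Month 1. These sizes rest on normal TIR with SD 20 and the assumed correlations and slopes; the existence of the unused data rests on the documents alone.

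**What to change.** In Section 15.1, fit a repeated-measures model with visit (Baseline, Months 1, 2 and 3), treatment, treatment-by-visit and an unstructured covariance in place of the single patient random effect. Keep the Month 3 difference in change from Baseline as the sole primary estimate. Use the same model for the continuous CGM metrics in Section 15.2, but not for HbA1c, which is not measured at Months 1 and 2.

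State also:

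- **One visit-assignment rule.** With ±10 days the windows are Days 20–54, 50–84 and 80–114, so they overlap on Days 50–54 and 80–84. The rule must also place any final assessment after early exit.
- **One minimum number of sensor days for post-baseline visits.** Section 15.1 sets five days for Baseline only. Section 8.4 offers a repeat sensor below five days at Months 1 and 2 but below seven at Month 3.
- **The missing-at-random assumption** that the model makes.

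The cost is SAP wording, some programming and ten covariance parameters (4 × 5/2) instead of two. No new data are collected, and the precision gain is small. The choices should be fixed before outcome data are examined.

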All participants must obtain Virta's standard medical approval from a Virta HCP and meet all eligibility criteria, as defined in Section 6, to participate in the study. Once the informed consent form (ICF) has been signed, the participant is formally enrolled in the study and a participant ID number will be assigned and recorded in the shared Virta and IDC study database (REDCap). Participants will be randomized 1:1 to either the BGM or CGM arm (Table 1) once a minimum of five days of blinded Libre Pro CGM data is confirmed by the participant. Of note, the blinded Libre Pro CGM system provides a way for the participant to see the number of days of data recording while the sensor is in use. If a participant wears a blinded Libre Pro CGM at baseline that does not capture at least 5 days of data, the participant will be provided the option to wear a repeat blinded CGM or choose to exit the study. Participants who capture five or six days of blinded CGM data may also be provided an option to wear a repeat blinded CGM to collect additional blinded CGM data.

Blinding procedures are not described since blinding is not possible in a study comparing two different methods of glucose monitoring (BGM versus CGM); the participants will know which arm they are assigned to in order to conduct the appropriate monitoring.

Given that enrolling participants takes several months to complete, a block randomization scheme will be used to ensure that participants are assigned to BGM and CGM arms in approximately equal proportions each month. The participant randomization schedule will be generated by the study statistician using the random number generator in SAS. Participants will remain in their assigned study arm throughout the intervention and follow-up period (day 0 to day 194).

Table 1. Randomization arms and associated study-arm devices

Study Arm	Devices Used
Blood Glucose Monitoring (BGM) Arm	Commercially approved FreeStyle Libre Pro Sensor and Reader (blinded CGM) Commercially approved Precision Xtra Blood Glucose & Ketone Monitoring System for glucose and ketone monitoring; used in accordance with package inserts.
Continuous Glucose Monitoring (CGM) Arm	Commercially approved FreeStyle Libre Pro Sensor and Reader (blinded CGM for baseline assessment only) Commercially approved 14-day, personal FreeStyle Libre 2 system and associated phone-based app; used in accordance with package inserts.

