15.5 Sample Size Determination

The sample size estimation is based on the following assumptions:

- 80% power (at 0.05 significance level) to test the primary hypothesis, which is the difference in TIR between BGM and CGM arms
- anticipated mean difference in TIR between CGM and BGM = 10%
- anticipated standard deviation of TIR in each arm = 20%

The two-sided t-test suggests N=63 for each arm. Assuming an 85% retention rate at the end of the 3-month Post-Dietary Change period brings the required sample size to approximately N=75 per arm; or N=150 randomized participants with adequate Baseline data.

Consented participants who are not randomized do not count toward the 150 total participants; these participants may be replaced.

16 Ethics/Protection of Human Subjects

This protocol and any amendments will be submitted to Advarra for formal approval of the study conduct. The decision of the IRB concerning the conduct of the study will be made in writing to the Investigator. A copy of the initial IRB approval letter will be provided to the study funder (Abbott Diabetes Care) before commencement of this study.

This study will be conducted in full accordance with all applicable Federal and state laws and regulations including 45 CFR, and the HIPAA Privacy Rule. Any episodes of non-compliance will be documented. The Investigators will perform the study in accordance with this protocol, will obtain consent, and will report unexpected problems in accordance with IRB policies and procedures. Collection, recording, and reporting of data will be accurate and will ensure the privacy, health, and welfare of research participants during and after the study.

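### The patient random effect in 15.1 and 15.2 forces one variance on Baseline and Month 3, so period-specific standard errors may be wrong, although the primary contrast is nearly unaffected

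*Combined protocol and SAP*

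**What the plan says.** Section 15.1 analyses time in range (TIR) with a linear mixed model containing treatment, period (Baseline and Post-Dietary Change), "interaction between treatment and period as fixed effects, and patient as random effect". It promises adjusted means per treatment with standard errors, and a treatment mean difference with standard error and 95% interval. It does not say whether that difference is the difference in change or the Month 3 difference. On testing it says "The statistical test will be two-sided tests at a nominal 5% significance level". Section 15.2 applies the same model to time above and below range, mean glucose, coefficient of variation, MAGE and HbA1c. Neither section names a period-specific residual variance, an unstructured covariance, a robust standard error or a transformation.

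Sections 4.1 and 4.2.1 define the primary outcome as change in TIR from Baseline to Month 3. Section 15.5 gives a single spread, "anticipated standard deviation of TIR in each arm = 20" percentage points, with no SD by period and none for change.

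**The concern.** A random patient intercept with one residual variance is a compound-symmetry model: with two periods, Baseline and Month 3 must have the same variance. That may not be so here. TIR is capped at 100% and time above 250 mg/dL is floored at zero. Both arms receive a program whose earlier trial averaged a 1% fall in HbA1c at 10 weeks (Section 3.1), and moving people toward a bound tends to shrink spread. If the variances differ, the model averages them and attaches the same average to each period.

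Two things are at stake. One is the validity of the standard errors of the promised adjusted means, and of any single-period arm difference. The other is how participants with Baseline data only are used. Section 15.1 requires only adequate Baseline data for inclusion and about 15% attrition is planned for, so such participants enter the model, and their contribution depends on the assumed covariance.

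**Working it through.** **Inputs from the documents.** Two-sided 5% level (15.1); "80% power (at 0.05 significance level) to test the primary hypothesis", "anticipated mean difference in TIR between CGM and BGM = 10" points and an SD of 20 points (15.5); 1:1 allocation (7.2); "Assuming an 85% retention rate at the end of the 3-month Post-Dietary Change period" (15.5).

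**Inputs that are assumptions.** The documents give no SD by period and no within-patient correlation ρ. The main case is SD 25 at Baseline, 15 at Month 3, ρ = 0.5. The range is Baseline SD 10 to 28, Month 3 SD 10 to 20, ρ 0.3 to 0.7.

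**The plan's own figure.** n per arm = 2 × (1.960 + 0.842)² × 20² / 10² = 62.8, so 63; 63 / 0.85 = 74.1, so 75 per arm and 150 in total. Both figures reproduce. (The exact noncentral t gives 79.5% power at 63 and passes 80% at 64, a rounding matter.) The calculation is a t-test, so the covariance model does not enter it.

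**Complete pairs, algebra.** Let s_A and s_B be the Baseline and Month 3 SDs and c their within-patient covariance, with n per arm. With c positive, the random-intercept REML fit estimates the common variance as (s_A² + s_B²)/2 and the covariance as c. Then:

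- Difference in change: model variance = (2/n)(s_A² + s_B² − 2c). This is the variance from a two-sample t-test on change, whatever the two SDs are.
- Month 3 difference or mean: model SE / true SE = √((s_A² + s_B²)/2) / s_B.
- Baseline difference or mean: model SE / true SE = √((s_A² + s_B²)/2) / s_A.

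**Numbers.** For 25 and 15, the pooled SD is √((625 + 225)/2) = 20.62, so the ratios are 20.62/15 = 1.37 and 20.62/25 = 0.82. For 24 and 16, it is √((576 + 256)/2) = 20.40, giving 1.27 and 0.85. A mixed-model fit to one complete simulated data set (SDs 25 and 15) confirmed the first line: interaction SE 2.8653, against 2.8653 from the t-test on change. In that data set the model gave 3.11 for both single-period differences, against 2.53 (Month 3) and 3.61 (Baseline) from the data.

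**With dropout, simulation.** Random-intercept REML, 75 per arm, random dropout, 4,000 replicates per row. Entries are model SE / empirical SE, with type I error in brackets.

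| SD Baseline → Month 3 (ρ = 0.5) | Dropout | Difference in change | Month 3 difference | Baseline difference |
|---|---|---|---|---|
| 20 → 20 | 15% | 1.01 (4.9%) | 1.01 (4.6%) | 1.01 (4.9%) |
| 25 → 15 | none | 1.00 (5.1%) | 1.34 (1.0%) | 0.82 (10.3%) |
| 25 → 15 | 15% | 1.03 (4.2%) | 1.39 (0.6%) | 0.83 (9.9%) |
| 25 → 10 | 15% | 1.07 (3.6%) | 1.97 (<0.1%) | 0.79 (12.1%) |
| 10 → 20 | 15% | 0.96 (6.1%) | 0.78 (12.1%) | 1.54 (0.3%) |

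Across all falling-spread scenarios with dropout, including arms with different Month 3 SDs, the ratios were 1.03 to 1.07, 1.38 to 1.97 and 0.79 to 0.86. At 24 → 16 with ρ = 0.35, separate runs gave about 1.3 for Month 3 and 0.84 for Baseline. In the 24 → 16 and 25 → 15 cases, an unstructured covariance brought the ratios to about 1.0 (Month 3) and 0.95 to 1.00 (Baseline).

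**Dropout that depends on baseline.** The model implicitly predicts a missing Month 3 value from Baseline with slope c divided by the common variance; the true slope is c / s_A². At 25 → 15 and ρ = 0.5, c = 0.5 × 25 × 15 = 187.5, so at complete-data values the slopes are 187.5/425 = 0.44 and 187.5/625 = 0.30. If dropout is tied to baseline in opposite directions by arm, the errors do not cancel. The difference in change is then biased by about 0.5 to 1.6 points across runs, with type I error 6.6% in the run with the largest bias. With equal variances the bias is about zero. With dropout tied to baseline in the same direction in both arms, the bias was 0.16 (24 → 16) and −0.04 (25 → 15), zero within simulation error.

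**The case against.** The strongest reply is that nothing the trial tests is damaged. The primary and the mixed-model secondary endpoints are all defined as changes, so the tested contrast is the interaction, whose standard error is right or nearly so. The Month 3 target endpoints use logistic regression and ketones use linear regression, so neither is touched. Absolute CGM values at Month 3 are exploratory and descriptive. Summary SDs by treatment and period will be reported, so a change in spread would be visible. The fall in spread is itself assumed: the HbA1c entry range of 7.0 to 11.5% narrows Baseline spread, and varied response could widen Month 3 spread. Dropout in opposite directions by arm is a constructed case that nothing in the documents suggests.

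Most of this stands. Two parts do not dispose of the point. Section 15.1 does promise adjusted means with standard errors. It also leaves the treatment mean difference unnamed, while Section 15.5 sizes the trial on a difference in TIR with the SD of TIR and not of change, so an analyst could report the Month 3 difference.

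A reader might go further and infer that every reported standard error is wrong, the primary test included, or that spread will shrink for all the secondary metrics. The documents support neither. The algebra clears the primary contrast with complete pairs. Mean glucose, coefficient of variation, MAGE and HbA1c are not percentages approaching a cap, and time below range starts near zero in hyperglycaemic entrants and could widen as glucose falls.

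**Conclusion.** The model as written imposes equal variance at the two periods, and the documents offer no support for that restriction. If the variances differ, the period-specific standard errors are wrong. If spread falls, they are too large at Month 3 and too small at Baseline, by factors of about 1.3 to 1.4 and 0.83 at the assumed SDs of 24 to 25 falling to 15 to 16. If spread rises, the direction reverses. These sizes rest wholly on assumed SDs and correlations.

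The primary test is not invalidated. Under 15% random dropout its standard error is 3 to 7% too large in the falling-spread scenarios and 4% too small in the rising one. The stress-case bias of 0.5 to 1.6 points compares with a planned effect of 10. The point matters little for the primary test and moderately for the adjusted means, or if the Month 3 difference were reported. It is worth acting on because the remedy costs almost nothing and is right whether spread falls, rises or stays the same.

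**What to change.** In 15.1 and 15.2, replace the patient random effect with an unstructured within-patient covariance over the two periods (separate Baseline and Month 3 variances and a covariance), fitted by REML with the same fixed effects. State that the treatment mean difference to be reported and tested is the treatment-by-period interaction.

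The cost is one phrase in each section, one line of code and one extra variance parameter, which 126 evaluable or 150 randomized participants carry easily. The sample size stays at 63 evaluable and 75 randomized per arm.
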